15.3.3. Assessment Window for Phase Conclusion

The 'Phase Conclusion' records in disposition data will be slotted based on [Table 8](#) (for Maintenance Phase conclusion records), [Table 9](#) (for Extension Phase conclusion records), and [Table 12](#) (for Thigh Injection Phase and Return to Gluteal Injection Phase conclusion records). However, if the discontinuation date is post-treatment per [Table 20](#), the record will be slotted to the last on-treatment visit within the same phase rather than follow up.

15.3.4. Assessment Window for Health Outcome Data

15.3.4.1. PIN / HAT-QoL / HIVTSQs / HIVTSQc / ACCEPT / Preference in Main Study

PIN, HAT-QoL, HIVTSQs, HIVTSQc, ACCEPT, Preference, reasons for oral bridging and preference questionnaire assessments will be assigned to analysis visits as follows:

1. Baseline will be defined as last available recorded value up to and including the Maintenance treatment start date (expected to be collected at Day 1). Baseline is not applicable for PIN, HIVTSQc and Preference assessments.
2. For post-baseline visits, if the nominal visit identifier as captured in the source dataset corresponds to a scheduled collection per the Time and Events Schedule (see Section 15.2 and Table 15) and the assessment is collected in the Maintenance or Extension Phase (per Table 18), then the nominal visit identifier will be kept as the analysis visit.
3. For post-baseline visits, if the nominal visit identifier is unscheduled or withdrawal, then the following procedure will be used:
 - a) Assign the assessment to a study phase according to Table 18. Proceed to step b if the assessment is assigned to the Maintenance or Extension Phase.
 - b) Identify the 'last nominal visit' with the HO assessment performed prior to the unscheduled/withdrawal visit to be slotted in the same phase.
 - c) The unscheduled/withdrawal visit will be slotted to the planned nominal visit subsequent to the 'last nominal visit' in the same phase. If the 'last nominal visits' does not exist (e.g. no records originate from a planned nominal visit), then the unscheduled/withdrawal visit will be slotted to the first planned nominal visit after Day 1 in the same phase. If the planned nominal visit subsequent to the 'last nominal visit' is not available, then the unscheduled/withdrawal visit will be slotted to the last planned nominal visit after Day 1 in the same phase.

Example 1, for HATQoL, the planned nominal visits are Day 1, Week 24, and 48. If a participant has the 'last nominal visit' (with HATQoL assessment) at Week 24 prior to withdrawal at Week 36, the withdrawal assessment will be slotted to the subsequent planned nominal visit of Week 48.

Example 2, for HATQoL, if there is unscheduled visit between Week 24 and Week 48. This unscheduled visit will be slotted to Week 48 per the rule. In this case, there are two assessments with analysis visit equal to Week 48 (i.e. the slotted value and the value at original nominal week 48 visit). The original nominal value will be selected for summary per the rule below for multiple records—see Section 15.3.5.1.

Table 15 Planned Nominal Visit of Health Outcome Data in Main Study

| Questionnaire | Day 1 | Week 8 | Week 24 | Week 48 | Week 152 |
|--|---|--------|---------|---------|----------|
| PIN | | X | X | X | X |
| HAT-QoL | X | | X | X | |
| HIVTSQs | X | | X | X | X |
| HIVTSQc | | | | X | |
| ACCEPT | X | | X | X | X |
| Preference | | | | X | |
| Reasons for Oral Bridging and Preference | | | | | X |
| NOTES: | Day 1 visits are recorded as "Baseline" visits in the database. | | | | |

15.3.4.2. Reasons for Continuation/Switch in Main Study

Reasons for Continuation/Switch assessments are planned to be taken at nominal Baseline (Day 1) visit only. The assessments taken within \pm 2 weeks window from maintenance phase treatment start date will be regarded as evaluable. The assessments taken outside this window will be excluded from the summary.

15.3.4.3. HIVTSQs/HIVTSQc/Preference in Sub-study

HIVTSQs, HIVTSQc, Preference Thigh Injection vs Gluteal Injection questionnaire assessments will be assigned to analysis visits as follows:

1. Sub-study Baseline will be defined as last available recorded value up to and including the date of first thigh injection. Baseline is not applicable for HIVTSQc and Preference Thigh Injection vs Gluteal Injection assessments as they are not planned to be collected during the Sub-study Baseline. In Sub-study Baseline value derivation for HIVTSQs, the assessments conducted in the main study will also be considered.
2. For post-baseline visits, if the nominal visit identifier as captured in the source dataset corresponds to a scheduled collection per the Time and Events Schedule (see Section 15.2) and the assessment is collected in the planned phase (per [Table 18](#), visits at/before Sub-study Week 16 belong to Thigh Injection phase, and visits after Sub-study Week 16 belong to Return to Gluteal Injection phase), then the nominal visit identifier will be kept as the analysis visit.
3. For post-baseline visits, if the nominal visit identifier is unscheduled or it is scheduled however not conducted in the planned phase (e.g. the sub-study Week 16 HIVTSQs assessment is conducted after the Week 16 gluteal injection and therefore belong to Return to Gluteal Injection phase), then this visit will be assigned to the planned visit in the same phase.

15.3.4.4. Tolerability of Injections (NRS) in Sub-study

After assigning the phases per [Table 18](#), the NRS assessments will be slotted to analysis visits per [Table 16](#).

Table 16 Assessment Window for NRS Data

| Phase | Assessment Window | Visit |
|---------------------|--|--|
| Sub-study Screening | Q8W: post-dose and on the Week -8 injection date Q4W: post-dose and on the Week -4 injection date | Q8W: Sub-study Week -8 Q4W: Sub-study Week -4 |
| | Q8W: (Week -8 injection date+1, Week -8 injection date+14), inclusive Q4W: (Week -4 injection date+1, Week -4 injection date+14), inclusive | Q8W: Sub-study Week -7 Q4W: Sub-study Week -3 |
| Thigh Injection | Post-dose and on the Day 1 injection date | Sub-study Day 1 |
| | (Day 1 injection date+1, Day 1 injection date+14), inclusive | Sub-study Week 1 |
| | Q8W: post-dose and on the Week 8 injection date Q4W: post-dose and on the Week 12 injection date | Q8W: Sub-study Week 8 |

| | | |
|-------------------|--|---|
| | | Q4W: Sub-study Week 12 |
| | Q8W: (Week 8 injection date+1, Week 8 injection date+14), inclusive Q4W: (Week 12 injection date+1, Week 12 injection date+14), inclusive | Q8W: Sub-study Week 9 Q4W: Sub-study Week 13 |
| Return to Gluteal | Post-dose and on the Week 16 injection date | Sub-study Week 16 |
| | (Week 16 injection date+1, Week 16 injection date+14), inclusive | Sub-study Week 17 |

15.3.5. Assessment Window for PK Concentration Data

15.3.5.1. Maintenance and Extension Phase Assessments

For PK concentration data at the withdrawal/unscheduled/LTFU Month 1 visits during the maintenance and extension phase (after assignment to study phase per [Table 18](#)), the visit will be slotted to the analysis visit per the following steps:

- Identify the ‘last nominal visit’ with the planned PK pre-dose assessment prior to the visit to be slotted during the same study phase
- Identify the nominal visit corresponding to the next planned pre-dose PK assessment visit (excluding visits with storage PK collection), that is subsequent to the ‘last nominal visit’ with PK pre-dose assessment during the same study phase. If the ‘last nominal visit’ during the maintenance phase does not exist, the first planned pre-dose PK assessment visit for the participant during the maintenance phase will be considered the nominal visit corresponding to the next planned pre-dose PK assessment. If the ‘last nominal visit’ during the extension phase does not exist, slot the PK assessment to the nominal visit of the next planned injection occurring on or after the date of the PK assessment during the extension phase.
- If the nominal visit corresponding to next planned pre-dose PK assessment visit is prior to/at Week 48 visit, the PK assessment at the unscheduled/withdrawal/LTFU Month 1 visit will be slotted to this nominal visit corresponding to next planned pre-dose PK assessment visit.
- Otherwise, the PK assessment at the unscheduled/withdrawal/LTFU Month 1 visit will be slotted to the earliest nominal visit from the following:
 - Nominal visit corresponding to the next planned pre-dose PK assessment visit
 - The nominal visit of the next planned injection occurring on or after the date of the PK assessment during the same study phase

If both the next planned pre-dose PK assessment visit and the next planned injection visit during the same study phase are not available, for example, withdrawal PK assessment taken after Week 96 for participants on Q8W arm, the PK assessment will be slotted to Week 100 visit.

During the maintenance and extension phase, the planned nominal visits for PK Pre-dose are Week 4B, 8, 16, 24, 32, 40, 48, 96, 152 for Q4W arm; and are Day 1, Week 4B, 8, 16, 24, 32, 40, 48, 96, 152 for Q8W arm while Day 1 is required only for those transitioning from ATLAS on Q4W injections and Week 4B is required only for participants transitioning from oral SOC and requiring oral CAB+RPV lead-in. In addition, the participants on Q8W arm have planned nominal visits at Week 9 and 41 for 1-week post-dose.

For participants requiring oral CAB+RPV lead-in, the planned injection visits are Week 4B, Week 8, continuing every 4 weeks for Q4W arm and continuing every 8 weeks for Q8W arm. For participants not requiring oral CAB+RPV lead-in, the planned injection visits are every 4 weeks starting from Day 1 for Q4W arm and every 8 weeks starting from Day 1 for Q8W arm.

Example 1: If a participant on Q8W arm has the 'last nominal visit' (with PK pre-dose assessment) at Week 24 and then withdraws around Week 28, with the last injection at Week 24 and a Maintenance Phase PK assessment labelled at 'LTFU Month 1', This PK assessment labelled as 'LTFU Month 1' will be slotted to the subsequent planned nominal visit of Week 32.

Example 2: If a participant on Q4W arm has the 'last nominal visit' (with PK pre-dose assessment) at Week 48 and then have an unscheduled Maintenance Phase PK assessment around Week 74. This assessment will be slotted to the next planned injection visit, Week 76.

There will be no slotting for planned nominal visits (i.e. analysis visit =visit).

15.3.5.2. Long-term Follow-up Phase Assessments

PK concentration data at nominal visits other than withdrawal/LTFU Month 1/LTFU Month 3/LTFU Month 6/LTFU Month 9/LTFU Month 12/Liver Event which have been assigned to the LTFU phase (according to [Table 18](#)) will be slotting to analysis visits per the following steps:

- Identify the 'last nominal PK visit' with the PK assessment performed prior to the visit to be slotted during the LTFU phase
- The PK assessments will be slotted to the nominal visit corresponding to the next planned LTFU PK assessment visit that is subsequent to the 'last nominal PK visit' during the LTFU phase. If the 'last nominal visit' does not exist, the PK assessment will be slotted per **Error! Reference source not found..**

There will be no slotting for planned PK nominal visits (i.e. analysis visit =visit): LTFU Month 1 or withdrawal, LTFU Month 3, LTFU Month 6, LTFU Month 9 and LTFU Month 12.

15.3.5.3. Sub-study Assessments

Unscheduled sub-study assessments will not be slotted to any analysis visit. There will be no slotting for planned nominal visits (i.e. analysis visit=visit).

15.3.6. Multiple Assessments within an Assessment Window

If after window assignment there are multiple valid assessments of a parameter within the same window, then the following hierarchy will be used to determine the value to be used for summary statistics of observed values:

For data other than health outcome/PK concentration:

1. the assessment closest to the window target Study Day;
2. if there are multiple assessments equidistant from the target Study Day, then the mean of these values will be used. For HIV-1 RNA, the geometric mean of the number of copies will be used as opposed to the arithmetic mean. For post-dose ECG, the assessment closest to the two-hour post injection will be used.

For Health outcome and PK concentration data, the following hierarchy will be used to determine the value to be used for summary statistics of observed values:

1. If there are multiple on-treatment assessments assigned to the same analysis visit, the assessment from the planned nominal visit will be used for summary statistics.
2. If there are multiple on-treatment assessments assigned to the same analysis visit and none originates from a planned nominal visit (e.g. two unscheduled/withdrawal nominal visits), then
 - a. the assessment closest to the window target Study Day will be used;
 - b. if there are multiple assessments equidistant from the target Study Day, then the earliest assessment will be used.

Assessments not chosen for use in summary statistics by this algorithm will still appear in the associated listings. Also, all applicable valid assessments, irrespective of proximity to the target study day, will be used when categorizing values across visits, such as 'maximum grade' or 'at any time', and for any algorithm that has specific rules for which observation to use (e.g. snapshot algorithm, LOCF or CVF identification).

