- e. Physical exams should be conducted as part of normal routine clinical care. Medical assessments include any decisions the study staff must make for participants management and/or care of participant.
- f. Height collected at Baseline Day 1 only.
- g. Measure vital signs after about 5 minutes of rest in a semi-supine position.
- h. A 12-lead ECG will be performed after resting in a semi-supine position for at least 5 minutes. ECGs will be performed pre-dose. For participants transitioning from ATLAS, the pre-dose Week 48 ECG can also serve as the ATLAS-2M Screening ECG. ECG pre-dose will be performed in triplicate at

Day 1. A 2-hour post-dose ECG will also be performed at Days 1 and Week 48 for participants receiving CAB LA + RPV LA with an allowable window of ± 30 minutes.

- i. Only SAEs related to study participation or to a concomitantly administered ViiV/GSK product will be collected between obtaining informed consent and administration of study drug at Day 1.
- j. On Day 1, the eC-SSRS is to be administered prior to randomization. The eC-SSRS will preferably be completed at the beginning of the visit following administration of other PROs required prior to injections. The eC-SSRS is not required during the Withdrawal visit if withdrawal occurs during the Extension Phase.
- k. Women of childbearing potential only. SR=serum, UR=urine. Pregnancy events will be captured starting at Day 1 following initial exposure to study drug. Urine pregnancy test performed at Day 1 prior to administration of study drug, at Week 4B, and at study visits when other blood draws are not required in order to limit needle sticks. Serum pregnancy test can substitute for urine pregnancy test if locally required but must be appropriately timed to confirm pregnancy status prior to randomization and first IM administration.
- l. Week 48, Week 96 and Week 152 HIV-1 RNA retest (within 4 weeks) for results > 50 c/mL will be captured as unscheduled visit. Plasma for storage samples will be used for possible future analyses.
- m. A morning specimen is preferred. To assess biomarkers: urine albumin/creatinine ratio; urine protein/creatinine ratio; and urine phosphate. Urine phosphate results from visit 4a are not required by protocol to inform the safety review at visit 4b prior to receipt of initial CAB LA + RPV LA injections.
- n. An overnight fast is preferred; however, a minimum of a 6-hour fast is acceptable.

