15.3. Appendix 3: Assessment Windows

15.3.1. Definitions of Assessment Windows for Analyses

Laboratory data, vital signs, ECGs, health outcomes assessments, and genotypic/phenotypic data will be assigned to assessment windows according to actual dates rather than the nominal visit labels as recorded on the eCRF or in the laboratory database.

In most cases the window around an assessment will include all dates from the midpoints between the target day and that of the previous and the proceeding visits. In general, the nominal target study day for week w is $(7*w)+1$.

For parameters which are not scheduled to be assessed at particular visits, the all-inclusive assessment windows will still be used; however, data summaries will only report scheduled visits. Assessments at unscheduled visits will be included for ‘any time On-treatment’ time points and in data listings, as well any algorithms that make use of additional data (e.g., Snapshot).

Prior to visit slotting, assessments are first assigned to a study phase (screening, maintenance, extension, sub-study screening, thigh injection, return to gluteal injection or long-term follow-up) based on the Tables in Section 15.4.1 and treatment state based on Section 15.4.2.

Maintenance phase assessments other than health outcome and PK are assigned based on the Study Day as shown in Table 8. Table 8 also includes visiting slotting for screening assessments. The analysis visits from Week 4 to Week 100 should be only applied to the assessments that are already assigned to Maintenance phase (on-treatment). Extension phase assessments other than health outcome and PK are assigned based on the Study Day as shown in Table 9. The analysis visits from Week 104 (except for Follow-up) in the Extension phase should be only applied to the assessments that are already assigned to Extension phase (on-treatment). The snapshot visits up to Week 152 during the Maintenance or Extension phase are assigned based on Study Day as shown in Table 10.

The sub-study assessments other than health outcome, PK and HIV-1 RNA are assigned analysis visits based on Study Day as shown in Table 11. The assessment visit windows for HIV-1 RNA data are defined in Table 12, and the snapshot windows for visits up to Sub-study Week 16 are defined in Table 13.

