15.3.2. Definitions of Assessment Windows for Analyses other than Health Outcome and PK

Table 8 Assessment Windows for Screening and Maintenance Phase Data

| All Parameters except for where noted ^[c] | Target Study Day | Analysis Window | Analysis Timepoint |
|---|-------------------------------|---|--------------------|
| | The study day of first record | Study Day ≤ 1 | Screening |
| | 1 | Last available recorded value up to and including the Maintenance treatment start date, excluding post-dose ECG taken on the Maintenance treatment start date | Baseline |
| ECG | 1 | Value taken post-dose on the Maintenance treatment start date | Day 1 (Post Dose) |
| Urinalysis ^[a] | 29 | 2 ≤ Study Day ≤ 70 | Week 4 |
| | | 2 ≤ Study Day ≤ 42 | |
| | 57 | 43 ≤ Study Day ≤ 84 | Week 8 |
| | 113 | 85 ≤ Study Day ≤ 140 | Week 16 |
| Urinalysis ^[a] , CD8, CD4/CD8 ratio | 169 | 141 ≤ Study Day ≤ 210 | Week 24 |
| | | 141 ≤ Study Day ≤ 196 | |
| | 225 | 197 ≤ Study Day ≤ 252 | Week 32 |
| | 281 | 253 ≤ Study Day ≤ 308 | Week 40 |
| Urinalysis ^[a] , fasting glucose, lipids ^[b] , CD8, CD4/CD8 ratio, weight, vital signs, ECG | 337 | 309 ≤ Study Day ≤ 378 | Week 48 |
| | | 309 ≤ Study Day ≤ 364 | |
| | 393 | 365 ≤ Study Day ≤ 420 | Week 56 |
| | 449 | 421 ≤ Study Day ≤ 476 | Week 64 |
| | 505 | 477 ≤ Study Day ≤ 532 | Week 72 |
| | 561 | 533 ≤ Study Day ≤ 588 | Week 80 |
| | 617 | 589 ≤ Study Day ≤ 644 | Week 88 |
| Urinalysis ^[a] , fasting glucose, lipids ^[b] , CD8, CD4/CD8 ratio, weight, vital signs, ECG | 673 | 645 ≤ Study Day ≤ 714 | Week 96 |
| | | 645 ≤ Study Day ≤ min (Study Day of Nominal Week100 Visit -1, 700) | |

| All Parameters except for where noted ^[c] | Target Study Day | Analysis Window | Analysis Timepoint |
|--|------------------|--|--------------------|
| | 701 | min (Study Day of Nominal Week 100 Visit, 701) ≤ Study Day ≤ (Study Day of Nominal Week 100 Visit) | Week 100 |
| If a participant permanently discontinued study treatment: | | | |
| | | For Participants on Q8W Arm: Date > max (Date of Last Dose of Oral Study Treatment (CAB+RPV or SOC Bridging) + 1, Date of Last Injection + 63) | Follow-up |
| | | For Participants on Q4W Arm: Date > max (Date of Last Dose of Oral Study Treatment (CAB+RPV or SOC Bridging) + 1, Date of Last Injection + 35) | |

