| ECG | 7*w + 1 | Value taken post-dose on the date of first thigh injection | Sub-study Day 1 (Post Dose) |
| Injection Site Reaction | 7*w + 1 | First thigh injection date ≤ Study Day ≤ max (7*w + 1, First thigh injection date +1) | Sub-study Day 1 |
| | 7*(w+8) + 1 | Min (7*w + 2, first thigh injection date+1) ≤ Study Day ≤ 7*(w+12) | Sub-study Week 8 |
| Urinalysis ^[a] , fasting glucose, lipids ^[b] , CD8, CD4/CD8 ratio, weight, vital signs, ECG | 7*(w+16) + 1 | 7*(w+12) + 1 ≤ Study Day ≤ 7*(w+22) | Sub-study Week 16 |
| | | 7*(w+12) + 1 ≤ Study Day ≤ 7*(w+20) | |
| | 7*(w+24) + 1 | 7*(w+20) + 1 ≤ Study Day ≤ 7*(w+28) | Sub-study Week 24 |
| If a participant permanently discontinued study treatment: | | | |
| | | For Participants on Q8W Arm: Date > max (Date of Last Dose of Oral Study Treatment (CAB+RPV or SOC Bridging) + 1, Date of Last Injection + 63) | Follow-up |
| | | For Participants on Q4W Arm: Date > max (Date of Last Dose of Oral Study Treatment (CAB+RPV or SOC Bridging) + 1, Date of Last Injection + 35) | |
| NOTES: | | | |
| 
 The “w” in the target study day calculation refers to the corresponding week number in Extension for the planned Sub-study Day 1 visit. For example, if a participant’s last planned Extension phase visit before entering the Sub-study is Week 192, the “w” would be 200 if the participant is on Q4W arm and would be 208 if the participant is on Q8W arm. Follow-up will be derived only for participants who permanently discontinued study treatment. Sub-study Day 1 (Post Dose), Sub-study Week 8 and Sub-study Week 16 visits are Thigh Injection phase visits, Sub-study Week 24 is Return to Gluteal Injection phase visit. | | | |
| [a] Urinalysis: All parameters provided by the central laboratory under the category of urinalysis, including Urine Albumin/Creatinine, Urine Creatinine, Urine pH, Urine Protein/Creatinine, Urine Erythrocytes, Urine Specific Gravity, Urine Leukocytes, Urine Retinol Binding Protein, Urine Phosphate, Urine Creatinine. | | | |
| [b] Lipids: Cholesterol, HDL Cholesterol Direct, LDL Cholesterol Calculation, LDL Cholesterol Direct, Total Cholesterol/HDL Cholesterol Ratio, Triglycerides | | | |
| [c] Analysis windows for parameters with sparse collection are noted. | | | |
| [d] The values considered for deriving Sub-study Baseline value include both Extension phase and sub-study data. | | | |

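### The SAP schedules a 2-hour post-dose ECG at Week 48 but defines no Week 48 post-dose timepoint, so the by-visit Week 48 ECG and QTc value is undetermined

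*SAP*

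**What the plan says.** - **Schedule.** Footnote h in Section 15.2.1 (Q4W arm) states: "A 2-hour post-dose ECG will also be performed at Days 1 and Week 48 for participants receiving CAB LA + RPV LA". Section 15.2.2 (Q8W arm) carries the same requirement. The footnote also asks for pre-dose ECGs.
- **Slotting.** Section 15.3.1 assigns ECGs to windows "according to actual dates rather than the nominal visit labels".
- **Windows.** Table 8 in Section 15.3.2 has one post-dose ECG row, Day 1 (Post Dose), defined as "Value taken post-dose on the Maintenance treatment start date". Post-dose ECGs are excluded from Baseline. The Week 48 row covers "309 ≤ Study Day ≤ 378" for ECGs, with no split by dose timing. Table 11 gives the sub-study its own post-dose row: "Value taken post-dose on the date of first thigh injection".
- **Ties.** Section 15.3.6 first takes the reading nearest the target day. After that, "if there are multiple assessments equidistant from the target Study Day, then the mean of these values will be used". The same numbered item ends by saying that, for a post-dose ECG, the one nearest two hours after injection is taken.
- **Related analyses.** Section 5.2 takes the ECG baseline from the last pre-treatment set. Table 6 in Section 11.1 plans a plot of change in pre-dose QTcF against drug concentration at Week 48 or 152.

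**The concern.** Two ECGs are planned on the Week 48 injection date, and they measure different things: one at the end of a dosing interval, the other two hours after an injection. Elsewhere the plan keeps these apart. Table 8 and the notes to Table 18 do so for main-study Day 1, and Table 11 and note [d] of Table 18 do so for Sub-study Day 1. Week 48 is the only scheduled post-dose ECG without a slot.

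At stake is what the Week 48 line of the by-visit ECG and QTc tables means. Baseline is pre-treatment, so a Week 48 value that contains a post-dose reading mixes dose timings and does not match the planned pre-dose QTcF analysis. If the post-dose reading is instead kept out of the Week 48 row, no timepoint is left at which to summarise it. This matters most for Group 1. These participants start on oral lead-in, and footnote h limits the post-dose ECG to participants receiving the injectable regimen, so Week 48 is their only scheduled main-study post-dose ECG. Group 2 is injected on Day 1 and has one there as well.

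**Working it through.** **1. The plan's target day.** Section 15.3.1 says that "the nominal target study day for week w is" 7w + 1. For Week 48: 7 × 48 + 1 = 337, which agrees with Table 8.

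**2. Do the two ECGs tie?** The distance to target is |Study Day − 337|. A pre-dose and a post-dose ECG on one injection date share a Study Day, so the distances are equal whatever that day is. The window has 378 − 309 + 1 = 70 days, and the pair ties on each of them. The nearest-to-target rule cannot separate the pair.

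**3. What happens to the tie?** The answer depends on how far the post-dose sentence in Section 15.3.6 reaches:

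| Reading of the post-dose sentence | Week 48 by-visit value | Consequence |
|---|---|---|
| (a) It acts only within a defined post-dose timepoint, and Table 8 has one only at Day 1 | Mean of the two readings | Dose timings are blended |
| (b) It acts on any post-dose ECG in a window | Post-dose reading | Pre-dose reading is displaced |
| (c) Post-dose ECGs are a separate series | Pre-dose reading | Post-dose reading has no Week 48 timepoint |

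The SAP does not say which applies. Under (a) and (b) the change from a pre-treatment baseline is not like for like. Under (c) it is, but the scheduled post-dose reading drops out of the by-visit summary.

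**4. How far apart are the readings?** Let the change from baseline be a pre-dose and b post-dose, with d = b − a. The mean is (a + b)/2 = a + d/2. It overstates the pre-dose change by d/2 and understates the post-dose change by d/2 when d is positive. The document gives no figure for d, so these inputs are assumptions:

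| Pre-dose a (msec) | Post-dose b (msec) | (a) Mean | (b) Post-dose | (c) Pre-dose |
|---|---|---|---|---|
| 0 | 20 | 10 | 20 | 0 |
| 10 | 70 | 40 | 70 | 10 |
| 50 | 80 | 65 | 80 | 50 |

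Against the plan's criterion of an increase of at least 60 msec (Section 8.4), the second participant meets it at that visit only under (b); the third meets it under (a) and (b) but not (c).

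**5. What is affected?** The by-visit ECG and QTc tables that include Week 48, for example change from baseline in ECG values by visit (Table 3.60 at Week 48, 3.65 at Week 96, 3.56 at Week 152). A Week 48 pre-dose QTcF plot would be affected if it drew on the windowed value. Section 15.3.6 keeps unselected readings in the listings and uses all valid readings for maximum and any-time categories.

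**The case against.** A reader might infer from the tie rule alone that the plan averages the two Week 48 readings. The document does not support that as the stated result. The item that sets the mean goes on to treat post-dose ECGs differently, and that sentence is tied to a type of reading, not expressly to Day 1. Table 6 also treats pre-dose QTcF at Week 48 as a quantity of its own, which sits badly with an intention to pool. This part of the objection stands: averaging is one of three readings.

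The sentence does not close the gap, however. It selects a post-dose ECG. It does not say where that value is reported at Week 48, or what becomes of the pre-dose reading on the same day.

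Three further points have weight:
- The by-visit tables refer to shells from other reporting efforts that are not in the document. Those shells may already separate the two timings, but the SAP text does not.
- It would be wrong to call Week 48 the only post-dose ECG after repeated injections. Group 2 enters on monthly injections and has a Day 1 post-dose ECG with its own slot.
- A reader might infer that a QTc signal could be missed. Listings and worst-value categories retain every reading. The adverse events of special interest are identified from coded terms and adverse event data, not from by-visit ECG means.

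**Conclusion.** The concern holds as a missing timepoint combined with a selection rule of unclear scope. Two scheduled readings share one Week 48 row and always tie, and the SAP does not determine whether the reported value is the mean, the post-dose reading or the pre-dose reading. Two of these outcomes mix dose timings in the change from baseline; the third leaves the post-dose reading with nowhere to be reported. That the readings are averaged is a possible outcome, not an established one.

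The gap concerns every participant with both Week 48 ECGs. Its size is d/2 in each direction if the mean is used and the full d if one reading stands in for the other; the value of d is not known from the document. The conclusion assumes both ECGs are taken on the injection date as scheduled and that no unscheduled ECG on another date lies nearer to Day 337. Only descriptive by-visit ECG and QTc summaries, and possibly a Week 48 pre-dose QTcF plot, are touched. The change should be made, but no efficacy result depends on it.

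**What to change.** 1. In Table 8, add a row assigning an ECG taken post-dose on the Week 48 injection date to a Week 48 (Post Dose) timepoint, and limit the existing Week 48 ECG row to pre-dose readings.
2. In Section 15.3.6, state that ties are resolved only among ECGs of the same dose timing, and that the two-hour rule selects within a post-dose timepoint.
3. Show Week 48 and Week 48 (Post Dose) separately in the by-visit ECG and QTc tables.

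The cost is one window row, a short clarification of the tie rule and one extra line per table. The schedule already provides for both ECGs, so no new data are needed.
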